^a The safety follow-up visit window will be restricted to assessments prior to the date of initiation of another investigational agent or hormonal therapy affecting the hypothalamic-pituitary-gonadal axis or surgical intervention for uterine fibroids

Table 4: Visit Windows for Week 24 Assessments (Transvaginal Ultrasound, Endometrial Biopsy, EQ-5D-5L)

Visit	Start Day	Target Day	End Day
Week 24	128	169	196
Safety Follow-up ^a	Date of last dose + 7 days	Date of last dose + 30 days	Date of last dose + 60 days

Abbreviations: EQ-5D-5L, European Quality of Life Five-Domain Five-Level.

^a The safety follow-up visit window will be restricted to assessments prior to the date of initiation of another investigational agent or hormonal therapy affecting the hypothalamic-pituitary-gonadal axis or surgical intervention for uterine fibroids.

Table 5: Time Window for eDiary and Feminine Product Collection

Visit	Feminine Product Collection Visit Date ^{a,b}	Time Window ^a
Week 4	X ₁	(Date of Study Day 1) - < X ₁
Week 8	X ₂	(X ₁ +1) - ≤ X ₂
Week 12	X ₃	(X ₂ +1) - ≤ X ₃
Week 16	X ₄	(X ₃ +1) - ≤ X ₄
Week 20	X ₅	(X ₄ +1) - ≤ X ₅
Week 24	X ₆	(X ₅ +1) - ≤ X ₆
Week 24/EOT	X _{Last} ^c	(Previous Feminine Product Returned Visit +1)] - ≤ X _{Last}

^a If feminine products are collected at more than 1 visit within a given visit window (Table 2), the last feminine product collection date will be used to define the time window. If the patient missed the previous visit, a planned study visit date will be used to calculate the window.

^b In the absence of feminine product collection due to amenorrhea the visit date when amenorrhea was reported will be used.

^c Date of last non-missing feminine product collection within the interval from (last dose date - 35) to (last dose date + 7 days) (see Section 7.3.3).

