7.3. Primary Efficacy Endpoint

The primary efficacy endpoint of the study is the proportion of women who achieve an MBL volume of < 80 mL AND at least a 50% reduction from Baseline in MBL volume over the last 35 days of treatment as measured by the alkaline hematin method. The primary endpoint will be referred to as responder rate and derived on the basis of the total MBL volume measured at the Week 24/EOT visit window taking into consideration the patient's compliance with return of feminine products and completion of the eDiary (see Section 7.3.2 and Section 7.3.4 for details).

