To ensure collection of all feminine products used during that menstrual cycle, an interval of up to 35 days for measurement of the primary endpoint was selected to accommodate women who continue to have cyclic bleeding on study treatment and whose natural cycle was at the upper end of the normal cycle duration range. This method is consistent with that used during screening for collection of feminine products. Specifically, the feminine product collection interval at Week 24/EOT is driven by types of bleeding patterns experienced by the patients, as described below:

- For patients who continue to have cyclic bleeding, the length of the interval depends on the duration of the patient's natural cycle; this is consistent with the way the Baseline MBL volume was determined (eg, the interval ranging from approximately 21 to 35 days);
- Patients who report irregular, non-cyclic bleeding are instructed to collect and return all feminine product used between study visits, up to 35 days, as per the schedule of events;
- For patients who report amenorrhea on the feminine production collection eCRF page, an interval of last 35 days of treatment will be reviewed to ensure that reported amenorrhea is not due to incomplete collection.

For patients who are in the midst of an episode of cyclic bleeding at the time of the Week 24/EOT visit, the visit window may be extended up to 7 days after the last dose of study drug to ensure patients return all used feminine products over that bleeding episode.

Per protocol, all used feminine products are to be collected at each visit and returned for analysis using the alkaline hematin method. For patients who continue to have menstrual bleeding, study visits are timed such that the feminine products used in the entire menstrual bleeding cycle are collected in one container provided at each visit.

MBL Volume at Week 24/EOT

MBL volume at Week 24/EOT is defined as the MBL volume obtained from the feminine product returned over the Week 24/EOT feminine product collection interval, as described above. The MBL volume at Week 24/EOT will be used to derive the primary efficacy endpoint.

If a patient did not return feminine product over the last 35 days of treatment and reported amenorrhea on the feminine product return eCRF page, she will be considered as amenorrhoeic and her MBL volume will be assigned as 0 mL.

Feminine Product Return Rate at Week 24/EOT

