7.3.5. Derivation of Responder Status at Week 24/EOT and Missing Data Handling Rules

For the evaluation of primary endpoint, missing data handling rules will be implemented for deriving responder status at Week 24/EOT as described below. The following elements will be checked: duration of treatment exposure; compliance with feminine product collection against the eDiary, as measured by FP RR; compliance with eDiary entry, defined as the proportion of eDiary entry days over the length (days) of FP collection interval for Week 24/EOT visit; and reasons for no FP collection (as displayed in [Table 7](#)).

Patients with < 4 weeks of treatment who withdraw from the study prematurely due to lack of efficacy or withdraw from the study prematurely to undergo surgical intervention for uterine fibroids will be considered as non-responders.

All other patients will have their responder status determined as follows:

- For patients with a FP RR of 100%, responder status will be determined based on the observed MBL volume;
- For patients who had incomplete feminine product collection, with a FP RR of < 100%, responder status will be derived based on either imputed or observed MBL volume;
 - Those with an MBL volume \geq 80 mL or < 50% reduction from Baseline will be considered as non-responders;
 - Those with an MBL volume < 80 mL and \geq 50% reduction from Baseline will be imputed for partial or complete missing MBL volume (see Section [7.3.6](#) for details).
- For patients who did not return a feminine product collection, responder status will be determined depending on the reason reported on the Feminine Product Collection eCRF:
 - If the reason is reported as Amenorrhea, the last 35 days of treatment will be used to derive responder status:
 - If the Week 24/EOT interval was 35 days, then she will be considered as a responder;
 - If the Week 24/EOT interval was <35 days, the following supportive information will be used to derive responder status:
 - If a patient reported amenorrhea at the visit prior to Week 24/EOT, she will be defined as a responder;
 - If a patient did not report amenorrhea at the visit prior to Week 24/EOT, eDiary data from the prior visit interval will be reviewed to confirm whether the patient was amenorrheic for a total of 35 days.

- If the eDiary from the previous interval confirms amenorrhea, then the patient will be considered as a responder;
- Otherwise, MBL volume will be imputed.

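### Responder status ignores the length of the Week 24/EOT interval when product is returned at full compliance and in the spotting branch

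*SAP*

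**What the plan says.** SAP Section 7.3 sets two criteria for response: MBL below 80 mL, together with "at least a 50% reduction from Baseline in MBL volume over the last 35 days of treatment as measured by the alkaline hematin method". Section 7.3.3 then takes the volume from product returned over the Week 24/EOT collection interval and says that "an interval of up to 35 days for measurement of the primary endpoint was selected". That is an upper limit only. For cyclic bleeders it gives, as an example, "the interval ranging from approximately 21 to 35 days". It adds that visits are meant to be timed so that a whole bleed falls in one collection, and that the window may be extended by up to 7 days after the last dose if the woman is in the middle of a bleed.

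Table 5 (Section 4.3.5) starts the interval at "Previous Feminine Product Returned Visit +1" and ends it at the last collection between 35 days before and 7 days after the last dose. Footnote a says that when product is collected at two visits inside one Table 2 window, the later date defines the window.

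The return rate (FPRR, Section 7.3.3) divides days with returned product by diary days of bleeding with product use, both counted inside the same interval.

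Three branches of Section 7.3.5 matter here:
- Product returned, full return rate: "For patients with a FP RR of 100%, responder status will be determined based on the observed MBL volume".
- No product, spotting or negligible bleeding: responder if diary entry exceeds 70%, with at most 5 days of bleeding with product use in total and at most 3 in a row over the interval.
- No product, amenorrhea: "If the Week 24/EOT interval was <35 days, the following supportive information will be used to derive responder status". The evidence is the report at the prior visit or the prior interval's diary. Failing both, the volume is imputed.

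Tables 7 and 8 carry no length condition in any branch. The 35-day check appears only in the text.

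**The concern.** Baseline MBL comes from one or two complete screening cycles. If the final interval covers only part of a cycle, a woman whose bleeding has not changed can show less than 80 mL and at least a 50% reduction because of visit timing. The plan recognises that a short interval is weak evidence, but acts on this only for women who report no bleeding. A woman who did bleed and returned product over the same short interval gets no such check. The result is a departure from the last-35-days definition in the primary endpoint, with some responders created by dates and not by treatment.

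**Working it through.** **1. The plan's own figure.** Section 2.2.1 gives 25% against 55%, two-sided 0.05, 130 per arm and about 20% dropout, hence 130 × 0.80 = 104 per arm. With the pooled chi-squared approximation, power = Φ[(d√n − 1.96√(2p̄(1−p̄))) / √(p₁(1−p₁) + p₂(1−p₂))] = Φ[(0.30 × 10.198 − 1.96 × 0.6928) / 0.6595] = Φ(2.58) = 99.5%. The stated value of at least 99% is reproduced, and this point disputes no number in the plan.

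**2. Which branches look at interval length (Section 7.3.5 text).**

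| Branch | Basis for responder status | Length checked? |
|---|---|---|
| Product returned, FPRR 100% | Observed volume | No |
| No product, spotting | Diary limits within the interval | No |
| No product, amenorrhea | Report, plus support if under 35 days | Yes |

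FPRR cannot stand in for the missing check. Numerator and denominator are confined to the same interval, so two bleeding days with two days of product give 100% however short it is.

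**3. Whether a short interval can arise.** Table 2 puts Week 8 at days 44 to 71 and Week 12 at days 72 to 99. A collection on day 57 and an early-termination collection on day 72 fall in different windows, so footnote a does not merge them. The interval runs from day 58 to day 72, that is 72 − 57 = 15 days. Adjacent windows abut throughout (Week 20 ends on day 155, Week 24 starts on day 156), so the minimum possible gap is 1 day.

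**4. What a short interval can do.** These assumptions are not in the SAP: 28-day cycle, 5-day bleed with flow 15/35/25/15/10%, 160 or 200 mL per cycle, bleeding unchanged, every start day equally likely, interval of 7 to 21 days. Product is returned and both criteria are met when the interval:
- ends on bleed day 1: 15% captured, 24 or 30 mL;
- starts on bleed day 4: 15 + 10 = 25% captured, 40 or 50 mL;
- starts on bleed day 5: 10% captured, 16 or 20 mL.

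The next smallest capture is 50%, or 80 and 100 mL, which fails the 80 mL limit. So 3 of 28 start days qualify, 10.7%. Once the interval covers the full 28 days the share is 0.

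With loss spread evenly over 5 to 7 days and Baseline of 100 to 300 mL, the share is 7 to 21% for a 28-day cycle and intervals of 7 to 21 days. For cycles of 21 to 35 days and intervals of 7 to 14 days it is 6 to 29%. A 35-day cycle still gives 6 to 17% at 21 or 28 days.

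**5. Effect on the planned comparison.** Let q be the share of true non-responders misclassified. In both arms the difference becomes (0.55 + 0.45q) − (0.25 + 0.75q) = 0.30 − 0.30q. In the active arm only it becomes 0.30 + 0.45q.

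| q (assumed) | Both arms | Power at 104 per arm | Active arm only |
|---|---|---|---|
| 2% | 29.4 points | 99.3% | 30.9 points |
| 5% | 28.5 points | 98.9% | 32.25 points |
| 10% | 27.0 points | 97.8% | 34.5 points |

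**The case against.** The best defence is that Section 7.3.3 already ties the interval to the natural cycle, times visits to the bleed, and allows a 7-day extension. Of the three qualifying start days, one is a visit on bleed day 1, which the extension could cover. The other two need the previous collection to have cut a period short, which the visit timing is meant to prevent. This lowers the frequency for visits on schedule. It does not close the gap, because the 21-to-35-day range is an example, the extension is optional, and none of it is a condition in Section 7.3.5 or in Tables 5, 7 and 8.

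Early terminators are also partly covered. Table 7 makes exposure under 4 weeks a non-response. Sensitivity Analysis 3 does the same for Week 4 to 12 discontinuations for specified reasons, and Sensitivity Analysis 4 keeps completers only. That stands, but neither sensitivity analysis is primary and none examines interval length.

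Two stronger readings are tempting. A reader might take a collection at Week 8 and termination 12 days later as the typical failure. Days 57 and 69 lie in one Table 2 window, and footnote a plausibly merges them, so the interval would reach back towards the Week 4 visit. A reader might also count every interval in which an unchanged woman shows little or no loss: 20/28 (71%) at 7 days, 17/28 (61%) at 10 and 13/28 (46%) at 14. All but 3/28 of each figure is intervals with no menses. Without product these go to the amenorrhea branch, which has its own check, or to the spotting branch. They count here only if spotting product is returned or the spotting branch applies.

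**Conclusion.** The gap is real but limited. For women with at least 4 weeks of exposure, the full-return and spotting branches assign responder status without regard to interval length, and intervals well short of a cycle are possible under Tables 2 and 5. About 11% (3/28) of unchanged women observed over such an interval would return menstrual product and be called responders. That figure rests on the assumed cycle, flow pattern and random timing, and applies only to women who have a short interval.

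The SAP does not say how many that is. It is probably few, mostly early terminators, and the 20% dropout assumption is not an estimate of it. A reader might infer bias in favour of the drug or a threat to power. The document supports neither: similar misclassification in both arms dilutes the difference, inflation needs it to fall mainly on the active arm, and power stays at 97.8% even with q = 10% in both arms. It is an inconsistency in the primary derivation that is cheap to correct.

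**What to change.** In Section 7.3.5 and Tables 7 and 8:
- If the Week 24/EOT interval is shorter than about 21 days (the SAP's own lower cycle figure), keep an observed volume of 80 mL or more, or a reduction under 50%, as a non-response. Otherwise treat the volume as partially missing and send it to the existing branch for return rates under 100%.
- Before the spotting branch assigns a responder, require the same minimum, or extend the diary check back to 35 days as the amenorrhea branch does.
- Add a sensitivity analysis of the primary endpoint by interval length. A 21-day cut-off does not cover longer cycles: in the illustration above, an interval of exactly 21 days still lets 3/28 through.

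The cost is some wording and one flag built from dates already held. The downside is that a few observed volumes are replaced by model predictions. The change belongs before unblinding, as Section 1 requires of analysis decisions.

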- If the reason is Other and the specification describes spotting or negligible bleeding, responder status will be defined as follows:

- The patient will be considered as a responder if it is supported by the eDiary data: the eDiary entry rate must exceed 70% and the patient must have reported no more than 5 total days of bleeding with product use and no more than 3 consecutive bleeding with product use over the collection interval.
- If the eDiary entries did not confirm spotting or negligible bleeding, but the patient had at least 8 weeks of MBL volume data prior to the Week 24/EOT visit, her missing MBL volume will be imputed to determine responder status. Eight weeks of MBL volume data represents a reasonable minimum length of observation to justify imputation of the remaining data in assessing the effects of hormonal therapy.
- Otherwise if the patient had < 8 weeks of MBL volume data, she will be considered as a non-responder;

- If the reason is any Other, the responder status will be derived as follows:

- If the patient had at least 8 weeks of MBL volume data prior to the Week 24/EOT visit, her missing MBL volume will be imputed and her responder status will be based on the imputed MBL volume.
- If the patient had < 8 weeks of MBL volume data, she will be considered as a non-responder.

Table 7: Derivation of Responder Status at Week 24/EOT and Missing Data Handling Rules – for Primary Analysis

Treatment Exposure	FP Collection (FPRR)	Observed MBL Volume	Reason for No FP Collection	Responder Status
< 4 weeks	N/A	N/A	N/A	Imputed as non-responder
≥ 4 weeks	100% FP Compliance	N/A	N/A	Based on the observed MBL volume
	<100% FP Compliance	MBL volume ≥ 80 mL or <50% reduction from Baseline	N/A	Imputed as non-responder based on the observed MBL volume
		MBL volume < 80 mL and ≥ 50% reduction from Baseline	N/A	Based on the imputed MBL volume
	No FP Collection	N/A	Reported “Amenorrhea”	Imputed as responder
			Reported “Spotting or negligible bleeding” and confirmed by eDiary ^a	Imputed as responder
			Reported “Spotting or negligible bleeding” although not confirmed by eDiary or any other reason, had at least 8 weeks of MBL volume data	Based on the imputed MBL volume
			The entries in the eDiary did not verify “Spotting or negligible bleeding” or any other reason and if had < 8 weeks of MBL volume data	Imputed as non-responders

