7.4.3. Derivation of Amenorrhea-Related Endpoints**Determination of Amenorrhea**

Rules for determining amenorrhea in the treatment period is defined as those who meet 1 of the following requirements for 2 consecutive visits (approximately 56 consecutive days). Patients will be deemed to have amenorrhea during a visit window according to the following rules:

- No feminine product returned due to reported amenorrhea in 2 consecutive visits

OR

- No feminine product returned due to other reasons or feminine product collection with a negligible observed MBL volume coupled with other data indicating infrequent non-cyclic bleeding/spotting as described in [Table 10](#).

Missing responses for menstrual bleeding questions in the eDiary will be treated as “No Bleeding” if eDiary compliance rate is > 70%.

Table 10: Rules for Determining Amenorrhea by Visit

Feminine Product Collection (KCAS) ^a	Supporting Data	
	Menstruation Status eCRF	eDiary
No feminine product collection due to reported amenorrhea	No menses start/stop dates reported	N/A
No feminine product collection due to other reasons	Per instructions for non-cyclic bleeding patterns, menses start date is reported but no menses stop date reported	
 • Data indicating infrequent, non-cyclic bleeding/spotting defined as bleeding/spotting with feminine product use for no more than 3 consecutive days and no more than 5 days bleeding total per visit window • eDiary entry rate > 70%
Feminine product collection with negligible observed MBL volume defined as <5 mL	Full or partial menses start and stop dates	
 • Data indicating infrequent, non-cyclic bleeding/spotting defined as bleeding/spotting with feminine product use for no more than 3 consecutive days and no more than 5 days bleeding total per visit window • eDiary entry rate > 70%

Abbreviations: eCRF, electronic case report form; eDiary, electronic diary; MBL, menstrual blood loss; N/A = not applicable.

^a There is no requirement for feminine product return rate, as the determination of amenorrhea is based on the eDiary response.

Amenorrhea During the Last 35 Days of Treatment

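### Reported amenorrhea with no product returned counts as 0 mL and primary response, and no rule tests it against the Week 24/EOT diary

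*SAP*

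**What the plan says.** **Reported amenorrhea, nothing returned.** Section 7.3.3 says of a woman with no return over the last 35 days: "she will be considered as amenorrhoeic and her MBL volume will be assigned as 0 mL". The same section sets her feminine product return rate (FPRR) to 100%. Section 7.3.5 then gives three routes:

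- Interval of 35 days: "If the Week 24/EOT interval was 35 days, then she will be considered as a responder".
- Shorter interval, with amenorrhea also reported at the previous visit: "If a patient reported amenorrhea at the visit prior to Week 24/EOT, she will be defined as a responder".
- Shorter interval, without such a report: "eDiary data from the prior visit interval will be reviewed to confirm whether the patient was amenorrheic for a total of 35 days". If that diary does not confirm amenorrhea, MBL volume is imputed.

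Table 7 has a single row for reported amenorrhea, without conditions: "Imputed as responder". Table 8 repeats it.

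**Reported spotting, nothing returned.** Section 7.3.5 requires diary support. It allows at most three days in a row of bleeding with product use and sets two further conditions: "the eDiary entry rate must exceed 70% and the patient must have reported no more than 5 total days of bleeding with product use". Without that support she is imputed if she has at least 8 weeks of MBL data, and is otherwise a non-responder.

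**Review.** For reported amenorrhea Section 7.3.3 says that "an interval of last 35 days of treatment will be reviewed to ensure that reported amenorrhea is not due to incomplete collection". Section 7.3.4 says responder status takes account of collection compliance and diary compliance over the same window.

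**Amenorrhea endpoint.** Table 10 has a row headed "No feminine product collection due to reported amenorrhea". Its supporting data are the absence of menses dates on the Menstruation Status eCRF, with the eDiary cell marked N/A. The rule must be met at two consecutive visits. The footnote to Table 10 says that amenorrhea is determined from the diary.

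**The concern.** The FPRR exists to compare what was returned with what the diary says should have been returned. For reported amenorrhea it is fixed at 100%, so the comparison is switched off in the one situation where nothing was returned and the whole result rests on an eCRF reason. The review in Section 7.3.3 is meant to fill that gap, but it names no data source, criterion or consequence, and Section 7.3.5 and Table 7 do not carry it out.

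The stronger claim, no bleeding at all, thus faces a weaker test than the milder claim of spotting. What is at stake is the classification of individual women on the primary endpoint. Section 7.4.2 applies the same rules to the responder rate by visit and to time to response.

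**Working it through.** **1. Does any branch read the Week 24/EOT diary?**

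| Reason for no return | Interval | Diary used | Result |
|---|---|---|---|
| Amenorrhea | 35 days | none | responder |
| Amenorrhea | under 35 days, amenorrhea at prior visit | none | responder |
| Amenorrhea | under 35 days, no amenorrhea at prior visit | prior interval only | responder if confirmed, otherwise imputed |
| Spotting or negligible bleeding | any | Week 24/EOT | responder if confirmed, otherwise imputed or non-responder |

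None of the three amenorrhea routes uses the Week 24/EOT diary. Table 7 also drops the third route, so text and table disagree for intervals under 35 days.

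**2. Two women with the same diary.** Each has a 35-day interval, diary entry above 70%, 6 days of bleeding with product use, and nothing returned. By the formula in Section 7.3.3 the FPRR would be 0/6 = 0%.

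- eCRF reason amenorrhea: FPRR set to 100%, MBL 0 mL, responder.
- eCRF reason spotting: 6 days exceeds 5, so not confirmed; FPRR set to 0; imputed with at least 8 weeks of MBL data, otherwise non-responder.

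One eCRF field decides the outcome.

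**3. Sensitivity analyses.** Analysis 1 changes which products count. Analysis 2 uses Table 8, which keeps the amenorrhea row. Analysis 3 changes the handling of early discontinuation. Analyses 4 and 5 change the population. Analysis 6 takes its missing cases from Tables 7 and 8 and keeps 0 mL for amenorrhea. None varies this rule.

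**4. The planning figure (Section 2.2.1).** Inputs: 25% on placebo, a 30-point difference (so 55% in Group A), two-sided 0.05, 130 per arm, 20% dropout. Then 130 × 0.8 = 104 per arm and the mean rate is 0.40. Standard error under the null: √(2 × 0.40 × 0.60/104) = 0.0679; under the alternative: √((0.25 × 0.75 + 0.55 × 0.45)/104) = 0.0647. Power = Φ((0.30 − 1.96 × 0.0679)/0.0647) = 0.995, or 0.992 with continuity correction. The stated figure of at least 99% holds and is not in dispute.

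**5. Which way could the bias go?** Assumption, not in the SAP: a share f of true non-responders return nothing and are recorded as amenorrheic, so they are scored as responders.

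- Same f in both arms: difference = (0.55 + 0.45f) − (0.25 + 0.75f) = 0.30(1 − f). For f = 5%, 10%, 20% this is 28.5, 27.0, 24.0 points, with power 0.989, 0.978, 0.939.
- f in Group A only: difference = 0.30 + 0.45f, that is 32.25, 34.5, 39.0 points.
- Extreme case, both true rates 25% and f in Group A only: the chance of a significant result in favour of Group A is about 9%, 22%, 64%, against 2.5%.

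For the whole planned difference to arise in this way, 0.25 + 0.75f = 0.55, so f = 0.40: two in five of Group A's true non-responders would have to be misrecorded, and none on placebo.

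**The case against.** The best defence is that the SAP does provide for a check. Section 7.3.3 commits to reviewing the last 35 days, Section 7.3.4 names diary compliance in the same window, and the opening of Section 7.3.5 lists it among the elements to be checked. On that reading the branches only extend an already reviewed interval to 35 days. This stands in part: the SAP shows the intention. But a programmer working from Section 7.3.5 and Table 7 would find no criterion to apply, and Table 7 attaches diary confirmation to the spotting row alone.

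It can also be said that amenorrhea is its own eCRF reason, whereas spotting is a specification under Other that concedes some bleeding and so needs quantifying. That explains a different test, but not ignoring a diary that contradicts the report. Two further cautions stand. Sparse diary entry contradicts nothing. And 6 diary days of bleeding do not prove non-response, since the endpoint is a volume below 80 mL with at least a 50% reduction.

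A reader might infer three stronger things that the document does not support:

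- *That the rule inflates the treatment difference.* This needs more false reports on active drug. That is plausible for a drug that suppresses bleeding, but the SAP does not establish it, and equal misreporting among non-responders would dilute the effect.
- *That every contradicted report is a lost response.* Under the existing rows, women with at least 8 weeks of MBL data would be imputed, and the model includes treatment, so some would remain responders.
- *That the amenorrhea endpoint is equally unguarded.* Table 10 requires two consecutive visits and no menses dates on a separate eCRF. Its defect is narrower: the N/A cell conflicts with the footnote.

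**Conclusion.** The concern holds for the primary endpoint. As written, bleeding with product use that the diary documents can be scored as 0 mL, FPRR 100% and response. This is more than missing detail, because the stated rule overrides evidence that Sections 7.3.3 and 7.3.4 say will be considered, and no sensitivity analysis would reveal it.

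The size cannot be given. The SAP does not say how many women fall in this branch or how often the diary disagrees, and the direction is equally open. The illustrations rest on assumed misreporting shares and show only that either direction is possible. If the planned 30-point difference is roughly right, reversal of the conclusion is unlikely; the estimates are what is exposed. The point should be fixed, but it does not invalidate the analysis.

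**What to change.** 1. **Section 7.3.5, Tables 7 and 8.** Give the review in Section 7.3.3 an effect. If the Week 24/EOT diary records bleeding with product use beyond the limits in footnote a of Table 7 (more than 5 days in total or more than 3 consecutive), do not accept reported amenorrhea. Do not set FPRR to 100% or MBL to 0 mL. Use the existing rows for reports not confirmed by the diary: impute with at least 8 weeks of MBL data, otherwise non-responder.
2. **Low diary entry.** Do not treat an entry rate of 70% or less as contradiction in the primary analysis.
3. **Sensitivity analysis.** Add one that scores as non-response all amenorrhea reports that the diary contradicts or cannot support (entry rate 70% or less).
4. **Table 7.** Align it with the text for intervals under 35 days.
5. **Table 10.** Reconcile the N/A cell with the footnote, and apply the same contradiction check in addition to the two-visit and no-menses-dates requirements.

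The cost is SAP wording, one programming condition on data already collected, and one added analysis, all to be settled before unblinding. Responder and amenorrhea rates may fall slightly.
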